4.7.1 Overall Survival

4.7.1.1 Definition of Endpoint

The overall survival (OS) will be calculated in months, defined as the time from the date of first study treatment administration to the date of death due to any cause. Participants not known to have died at the time of the analysis will be censored on the date they were last known to be alive.

OS time (months) = (date of event/censored - date of first study treatment administration + 1) / 30.4375.

4.7.1.2 Main Analytical Approach

OS will be summarized for both EAP study treatment groups and historical control groups based on the FAS.

The number and percentage of participants with event or censored will be presented by treatment group. The Kaplan-Meier estimates of the quartiles of the survival distribution along with corresponding 95% confidence intervals will be calculated. The survival rate (%) and 95% CI will be displayed for 2 months, 4 months, 6 months, 7 months, and 8 months.

To assess the differences in OS between PS matched (based on the pre-specified caliper width for main analysis) Trehalose group and historical control group: the hazard ratio (HR) and corresponding 95% confidence interval will be estimated using the Cox proportional-hazards model, stratified by PS matched ID. The two-sided log-rank test stratified by PS matched ID will be performed for generation of the two-sided p-value, which will be considered statistically significant if $p < 0.05$. The Kaplan-Meier plot for Trehalose and historical control groups will be presented.

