The clinical safety profile of trehalose and the nonclinical toxicology data support the investigation of SLS-005 as a potential treatment of ALS. Weekly dosing of SLS-005 is the only regimen to be evaluated in clinical trials to date (participants with OPMD and SCA3) and will be used in this trial. Participants with either sporadic or familial ALS accumulate TDP43 and participants with the superoxide dismutase (SOD) mutation accumulate SOD aggregates and thus have the potential to benefit from treatment with SLS-005 through activation of autophagy.

The is an intermediate expanded access protocol (EAP) trial to provide access to the investigational product, SLS-005, to participants with ALS who are not eligible to participate in clinical trials. The results might be included in a regulatory submission.

This statistical analysis plan (SAP) describes the detailed procedures for the planned statistical analyses of the efficacy, safety, and biomarker data that are collected. The endpoints are defined, and the statistical methods used to analyze them are presented. Table shells for the planned tables, figures, and listings (TFL) are included in a separate document, entitled “Data Presentation Plan” (DPP).

This version of the SAP has been developed using protocol version 1.0, dated 31 July 2023. Changes from the statistical methodology planned in the protocol are described in Section 7.

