2. STATISTICAL HYPOTHESES AND MULTIPLICITY ADJUSTMENT

No formal hypothesis testing will be conducted in this study. All analyses will be descriptive in nature. Any modeling that is performed will focus on parameter estimation. The Trehalose treated EAP participants will be compared to predicted placebo progression using historical controls, the p-values will be included to characterize associations and treatment effect but will mainly be used for the exploratory purpose and will not be adjusted for multiplicity.

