4.7.2.4 Supplementary Analyses

The following analyses will also be performed for the participants in PPS, using the same approaches as described above.

- ALSFRS-R total score summary for EAP study by treatment cohort and overall
- ALSFRS-R total score comparison between PS matched (based on the pre-specified caliper width for main analysis) Trehalose group and historical control group
- ALSFRS-R total score comparison between PS stratification-based Trehalose group and historical control group

In addition, an analysis of the total ALSFRS-R score will be performed using a general linear mixed effects model to compare the rate of decrease (ie, slope) of total ALSFRS-R scores over the 24-week treatment period between the PS matched (based on the pre-specified caliper width for main analysis) Trehalose and historical control, and between the PS stratification based Trehalose and historical control, respectively, for both FAS and PPS.

The model will fit a random intercept and slope for each participant and will include fixed effects for treatment group, bulbar onset (Yes/No), visit, and treatment by visit interaction. For comparison between the PS matched Trehalose and historical control, PS matched ID will be included as random effect; for comparison between PS stratification-based Trehalose and historical control, the PS stratification-built strata will be included as fixed effect.

An unstructured covariance structure will be used to model the within-participant errors. Visit will be expressed in weeks as a continuous variable and will include all scheduled visits including baseline as Week 0 (i.e., Week 0, Week 3, Week 12, Week 24). Missing values will not be imputed.

Estimates of the slope will be presented by the treatment group along with corresponding 95% CIs. The estimate of the difference between slopes (Trehalose vs. historical control) and the 95% CI of the difference between slopes will be presented. The null hypothesis of no difference in slopes between the treatment groups will be determined by testing the significance of the treatment by visit interaction term.

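### The SAP rules out formal hypothesis testing but sets a p < 0.05 significance rule for overall survival and a significance test of the ALSFRS-R slope, both against non-randomised controls

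*SAP*

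**What the plan says.** SAP Section 2 gives the general rule: "No formal hypothesis testing will be conducted in this study. All analyses will be descriptive in nature". It continues: "Any modeling that is performed will focus on parameter estimation". On the comparison with historical controls, it says that the p-values "will mainly be used for the exploratory purpose and will not be adjusted for multiplicity".

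Section 4.7.1.2 covers the main OS comparison between matched trehalose and historical control participants. It specifies a log-rank test, with each matched pair as a stratum, "for generation of the two-sided p-value, which will be considered statistically significant if" p < 0.05. Section 4.7.1.3 runs its sensitivity comparisons by similar approaches, and Section 4.7.1.4 runs the per-protocol comparisons by the same ones, so the rule carries over by reference.

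Section 4.7.2.4 compares ALSFRS-R slopes. After providing for the slope difference and its 95% CI, it ends by stating a null hypothesis, which "will be determined by testing the significance of the treatment by visit interaction term". No alpha is given.

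The ALSFRS-R repeated-measures analysis (Section 4.7.2.2) and the vital capacity analysis (Section 4.7.3.2) report a difference, a 95% CI and a p-value, with no threshold.

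On possible use, SAP Section 1 says: "The results might be included in a regulatory submission".

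**The concern.** A named test with a threshold, or a stated null settled by significance, is hypothesis testing. Section 2 says there will be none. A reader of the final report would not know which part governs, and the specific text on an endpoint is often taken to override the general text.

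The conflict falls on the endpoint that protocol Section 9.0 ranks first among the clinical efficacy measures. The comparison cannot support an error-rate statement. The SAP acknowledges that there is no randomised control group (Section 4.2), that matching balances only the covariates included (Section 4.2.3) and that stratification assumes no unobserved confounders (Section 4.2.4). At stake is how the report may describe a small p-value for survival in a document that might reach a regulator.

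**Working it through.** **1. The statements side by side.**

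| SAP section | Analysis | p-value | Decision rule |
|---|---|---|---|
| 2 | All | Mainly exploratory, unadjusted | None; no formal testing |
| 4.7.1.2 | OS, matched | Stratified log-rank, two-sided | Significant if p < 0.05 |
| 4.7.1.3, 4.7.1.4 | OS, other comparisons | As above, by reference | Inherited |
| 4.7.2.2 | ALSFRS-R change | Reported | None |
| 4.7.2.4 | ALSFRS-R slope | Interaction test | Null settled by significance; no alpha |
| 4.7.3.2 | % predicted VC change | Reported | None |

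The OS and slope sentences differ both from Section 2 and from the sections on the neighbouring endpoints. SAP Section 7, on changes from the protocol, deals only with the parent-trial data. Protocol Section 9.0 sets no significance level for the clinical comparisons.

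**2. How far the wording reaches.** Sections 4.7.1.2 to 4.7.1.4 name seven comparative survival analyses. In the FAS these are matched OS, stratified OS, and stratified OS including permanent assisted ventilation (PAV). In the PPS they are matched and stratified versions of both OS and OS including PAV. Other caliper widths and the unstratified fallback are extra. The slope comparison runs four ways: matched and stratified, each in FAS and PPS.

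**3. The plan's own figures.** SAP Section 6 gives power for neurofilament light only. It states no power, event count or alpha for OS or the slope. The neurofilament figure reproduces: for a 12% decline, delta = |ln 0.88| = 0.1278 and SE = 0.30/√70 = 0.0359, so power at two-sided 0.05 is about 94.6% (normal approximation), against a stated figure above 90%. That calculation is not affected by this point.

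**4. Size if the rule is applied (illustration).** The inputs are the two affected tests, OS and slope, each read at two-sided 0.05. The 0.05 for the slope is an assumption, because Section 4.7.2.4 gives none.

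- Upper bound under any dependence: 2 × 0.05 = 10%.
- If independent: 1 − 0.95² = 9.75%.
- Counting only false results that favour trehalose: at most 2 × 0.025 = 5%; if independent, 1 − 0.975² = 4.9%.

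**5. Residual confounding (assumed values, none in the documents).** With no drug effect and a residual hazard ratio HR due to population differences, the chance of p < 0.05 favouring trehalose is roughly Φ(√(events/4) × |ln HR| − 1.96). This treats the test as a simple 1:1 log-rank.

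| Total events | HR 1.0 | HR 0.8 | HR 0.7 | HR 0.6 |
|---|---|---|---|---|
| 20 | 2.5% | 7.2% | 12.3% | 20.7% |
| 40 | 2.5% | 10.5% | 20.3% | 36.5% |

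For example, with 20 events and HR 0.7: √5 × 0.3567 − 1.96 = −1.16, and Φ(−1.16) = 12.3%. Confounding could equally run against trehalose. The table shows only that the nominal 0.05 need not hold in this comparison.

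**The case against.** The best defence is that Section 2 must be read whole. It expects p-values against historical controls, calls them mainly exploratory and says openly that they are unadjusted. The endpoints are headed exploratory, there is no statistical primary endpoint (Section 4.5) and no secondary analysis (Section 4.6), and the limits of the matching are stated. Deleting a threshold changes no output, and a reader can infer significance at 0.05 from the 95% CIs anyway.

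Most of this stands and limits the severity. It does not remove the conflict: Section 2 says only mainly, and the OS rule carries no qualifier.

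The same facts rule out some stronger readings:

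- A reader might infer that the SAP declares survival significant or plans an efficacy claim. It does neither. It sets a conditional rule, and Section 1 says only that results might be used in a submission.
- A reader might infer that multiplicity is concealed, or that Section 2 calls testing impossible. The lack of adjustment is disclosed, and Section 2 says only that formal testing will not be conducted.
- A reader might count every efficacy comparison at 0.05 and quote 1 − 0.95³ = 14.3% for three or 1 − 0.95⁶ = 26.5% for six. The documents do not support those figures. The repeated-measures and vital capacity analyses state no threshold. The stratified and slope versions re-analyse the same endpoints in overlapping participants, so independence is implausible. The figures also count false results in both directions.

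**Conclusion.** The inconsistency is real and unresolved within the SAP. It affects what the report may conclude on the first-ranked clinical endpoint, so it is more than clerical, but it alters no model, estimate, interval or p-value. It should be corrected, as a matter of moderate rather than critical weight.

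The 10% ceiling in step 4 rests on reading exactly two tests at 0.05. It leaves out the further versions counted in step 2 and any residual confounding, and it is not an estimate of the study's actual error rate. The conclusion rests on the conflicting text and does not depend on that figure.

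**What to change.** Make three wording changes to the SAP.

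1. In Section 4.7.1.2, end the sentence after the p-value by deleting the significance clause and its p < 0.05 threshold. The sections that refer back then inherit no rule.
2. In Section 4.7.2.4, delete the last sentence. The slope difference and its 95% CI are already provided for just before it, so nothing needs to be added.
3. In Section 2, replace the qualifier mainly with a plain statement that *all p-values are nominal and support no claim of statistical significance*.

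If outputs have already been produced under the finalised SAP, the same statement can be placed in the report and table footnotes. The cost is a few sentences and the loss of a nominal significance claim. No analysis needs to be rerun.

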4.7.1.3 Sensitivity Analyses

To assess the treatment effect in OS, the following sensitivity analyses will be performed using similar approaches as described in the main analysis:

- OS comparison between PS matched (based on other caliper widths if available) Trehalose group and historical control group, including PS matched ID as stratification factor
- OS comparison between PS stratification-based Trehalose group and historical control group, including PS stratification-built strata and bulbar onset as stratification factors

Besides, for EAP study Trehalose group, the OS will also be evaluated by including the usage of permanent assisted ventilation (PAV) as event outcome together with death. A participant will be classified as having an event or being censored based on the earliest occurrence of outcomes as outlined in Table 4. The analytical approach will be the same as the approach detailed in Section 4.7.1.2.

Table 4 Censoring Rules for OS (Including PAV)

Scenario	Date of Event or Censored	Event or Censored
Usage of PAV	Date PAV started	Event
Death	Date of death	Event
Others	Date of last known to be alive	Censored

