Regimen E screening will also be utilized for final analyses. TEAEs will be summarized by the number of events of a given classification experienced by participants in each cohort and treatment group and by the number and proportion of participants experiencing such an event in each cohort and treatment group. The number of events and proportion of participants experiencing TEAEs will be summarized without regard to MedDRA term for any TEAE, any serious TEAE, any severe TEAE, any related TEAE, and any TEAE leading to discontinuation of study drug. TEAEs will be summarized by MedDRA system organ class and preferred term for the following groups of TEAEs: all TEAEs, serious TEAEs, severe TEAEs, related TEAEs, and TEAEs leading to discontinuation of study drug. TEAEs and serious TEAEs will also be summarized by MedDRA system organ class and preferred term by cohort, treatment group, and time after randomization in the following intervals: 0 to 24 weeks (168 days), 24 to 48 weeks (336 days), and 48 to 72 weeks (504 days) or longer.

Clinical efficacy analyses (Aim 2): The median survival, decline of ALSFRS-R and SVC (in that order of priority) of IV trehalose treated EAP participants (Cohorts 1, 2) will be compared to predicted placebo progression using historical placebo controls. Such a historical placebo comparison group will be created using the pooled resource open access clinical trials (PRO-ACT) and the Natural History Consortium Study in ALS databases, which are available to the PIs will be used for completing these analyses. Propensity score stratification or model-based prediction approaches will be used for placebo control group creation from these databases. Both visual inspection and a time-to-event analysis (survival) or repeated measures analysis (ALSFRS-R and VC) will be used to compare the two groups.

For each participant in the EAP and historical control analysis data set, we will estimate their propensity score and calculate a propensity score stratification factor. Additionally, for each participant treated in the EAP, we will create a set of model-based predicted placebos. Each treated participant together with their model-based predictions will define a model-based stratification factor. Both propensity score and model-based prediction analyses will utilize a set of baseline covariates that are included in both the historical control database and the EAP.

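### As written, the PS-stratified survival comparisons would show unadjusted Kaplan-Meier figures for the historical controls beside a stratum-adjusted hazard ratio

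*SAP*

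**What the plan says.** **Output planned for overall survival.** SAP 4.7.1.2 opens with "OS will be summarized for both EAP study treatment groups and historical control groups based on the FAS". It then lists:

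- quartiles: "The Kaplan-Meier estimates of the quartiles of the survival distribution along with corresponding 95% confidence intervals will be calculated";
- landmark rates: "The survival rate (%) and 95% CI will be displayed for 2 months, 4 months, 6 months, 7 months, and 8 months";
- a plot: "The Kaplan-Meier plot for Trehalose and historical control groups will be presented";
- a hazard ratio that "will be estimated using the Cox proportional-hazards model, stratified by PS matched ID", with a log-rank test stratified in the same way.

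Only the hazard ratio and the log-rank test are stratified.

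**Carry-over.** In 4.7.1.3, "the following sensitivity analyses will be performed using similar approaches as described in the main analysis". One of these analyses is the "OS comparison between PS stratification-based Trehalose group and historical control group, including PS stratification-built strata and bulbar onset as stratification factors". SAP 4.7.1.4 adds PS-stratified comparisons of OS (Including PAV) in the FAS, and of both OS definitions in the PPS.

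**How the strata are built.** SAP 4.2.4 cuts at the PS quintiles of the trehalose participants and drops a stratum only if one group is absent from it. The strata are then used as a stratification factor when the treatment effect is estimated. SAP 4.2.2 assesses PS overlap but gives no rule for trimming. Neither document mentions stratum weights, adjusted survival curves or Kaplan-Meier output by stratum.

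**Protocol.** Section 9.0, Aim 2, ranks the quantities to be set against historical controls, with median survival first: "The median survival, decline of ALSFRS-R and SVC (in that order of priority) of IV trehalose treated EAP participants".

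**The concern.** Stratifying a Cox model or a log-rank test removes between-stratum differences from the hazard ratio and the test. It does nothing to a Kaplan-Meier curve pooled over strata.

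In the matched analysis this is harmless. Unmatched people are excluded, so a plain curve for each group already compares similar case mixes. PS stratification keeps everyone in a retained stratum. Cutting at the trehalose quintiles equalises the trehalose counts over strata and leaves the control counts free. If controls cluster in the low-PS strata, their pooled curve describes patients with a different prognosis.

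The same table could then show a clear survival gap with no drug effect, in either direction, next to a hazard ratio near 1. The other PS-stratified endpoints do not have this problem. For ALSFRS-R (4.7.2.3) and % predicted VC (4.7.3.3) the strata are fixed effects in the model, so the least-squares means are stratum-adjusted as well as the differences. SAP section 1 says the results might go into a regulatory submission.

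**Working it through.** The plan gives no figure for survival, so there is nothing to reproduce. The check has three steps.

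**1. Who is in the stratified control group.** Strata are cut at the trehalose quintiles, so each contains trehalose participants by construction. The drop rule can therefore remove a stratum only when it holds no controls, and so it removes no control. With no trimming rule stated, the control group is the whole eligible historical set.

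**2. What pooling does when the drug has no effect.** Let S_k be survival in stratum k, the same in both groups. Pooled survival is the sum over k of (share of the group in stratum k) × S_k. The trehalose shares are 20% each (SAP 4.2.4). Control shares and S_k are assumptions, because the documents give neither.

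Middle case: 6-month S_k = 95, 92.5, 90, 85, 80%; control shares 50, 20, 15, 10, 5%.

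- Trehalose: (95 + 92.5 + 90 + 85 + 80)/5 = 88.5%.
- Control, pooled: 0.50×95 + 0.20×92.5 + 0.15×90 + 0.10×85 + 0.05×80 = 92.0%.
- False gap: 3.5 points against trehalose.
- Control weights, 20% divided by the control share: 0.40, 1.00, 1.33, 2.00, 4.00. Weighted control survival is 0.20 × (95 + 92.5 + 90 + 85 + 80) = 88.5%, so the gap is 0.

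Direction: reverse the gradient (80, 85, 90, 92.5, 95%) and keep the shares. Pooled control survival becomes 0.50×80 + 0.20×85 + 0.15×90 + 0.10×92.5 + 0.05×95 = 84.5%, against 88.5% for trehalose. The false gap is now 4.0 points in favour of trehalose.

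False 6-month gap, in points, over the other assumptions:

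| S_k (%) | Even shares | 35/25/20/12/8 | 50/20/15/10/5 | 70/15/8/5/2 |
|---|---|---|---|---|
| 94, 92, 90, 88, 86 | 0 | 1.3 | 2.0 | 2.9 |
| 95, 92.5, 90, 85, 80 | 0 | 2.5 | 3.5 | 4.9 |
| 97, 94, 90, 82, 70 | 0 | 4.3 | 5.9 | 8.1 |

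**3. Simulation with no drug effect.**

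- *Middle case above*, 70 trehalose and 500 controls, 300 data sets. Mean 6-month Kaplan-Meier survival was 88.4% for trehalose, 91.9% for controls unweighted and 88.3% for controls weighted. The stratified hazard ratio was 0.97 to 0.99 (mean and median); the unstratified one was about 1.42.
- *Estimated PS*, 70 trehalose and 400 controls, about 15% control mortality by 8 months, six prognostic covariates all shifted the same adverse way, 300 data sets per row:

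| Shift (SD) | Trehalose, 8 months | Control unweighted | Control weighted | Gap before → after |
|---|---|---|---|---|
| 0.20 | 81.4% | 85.3% | 81.9% | 3.9 → 0.5 |
| 0.35 | 77.7% | 85.3% | 79.3% | 7.6 → 1.6 |
| 0.50 | 74.2% | 85.1% | 75.6% | 10.9 → 1.4 |

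  The stratified hazard ratio was 1.00 to 1.07 and the crude one 1.25 to 1.83.
- *Mixed directions*, same group sizes, log-hazard 0.25 per SD, 150 data sets. With four covariates shifted one way and two the other, the unweighted gap was 1.8 points (0.20 SD) and 2.5 points (0.35 SD). With a three/three split at 0.35 SD it was 0.9 points.
- *Further runs* with 200 or 400 controls gave unweighted gaps from about 0, when the shifts cancel, to 13 points, when all go one way. Weighting left about 0 to 2 points.

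**The case against.** **The SAP never says the curves are unadjusted.** A reader might infer that it commits to presenting crude survival as a PS-adjusted result. The documents do not support that. The point follows from the reuse of similar approaches together with silence on adjustment. The SAP writes of the same approach elsewhere, so similar may leave room. The plot sentence stands in the paragraph on the matched comparison, and the table shells are in a separate Data Presentation Plan that is not available here. This stands as a limit on certainty. It does not remove the point, because nothing in the written plan would lead a programmer to adjusted curves.

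**Aim 2 median survival.** A reader might infer that the protocol's first-ranked quantity is compromised. It is not: the matched main analysis supplies a median from groups for which plain Kaplan-Meier is reasonable. The median may also not be reached. Under a constant hazard, the simulated 8-month trehalose survival of 74.2% and 81.4% gives medians of 8 × ln 2 / −ln(0.742) ≈ 19 months and 8 × ln 2 / −ln(0.814) ≈ 27 months, while the planned rates stop at 8 months. In practice the landmark rates and the plot are what a reader would use.

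**Size.** The all-one-way simulation alone would suggest a distortion of 4 to 11 points. That range comes from its assumptions. With mixed shifts the gap was 0.9 to 2.5 points, and with controls spread evenly it is 0.

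**Status and disclosure.** SAP section 2 calls the analyses descriptive and the p-values mainly exploratory, and this is a sensitivity comparison. SAP 4.2.4 and 4.4.3 provide balance checks and standardised differences for the stratified groups. These would warn a reader of a differing case mix, but they do not correct the curve.

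**Mismatch in the remedy.** The hazard ratio is stratified by PS stratum and bulbar onset, whereas the weights use PS stratum alone. This is correct. Bulbar onset enters the weights only through the PS, and the SAP should say so.

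**Conclusion.** The concern holds for the PS-stratified OS and OS (Including PAV) comparisons in 4.7.1.3 and 4.7.1.4. As written, their control quartiles, 2 to 8 month rates and plot would be those of the unweighted eligible control pool, shown beside a stratum-adjusted hazard ratio. The matched main analysis is not affected, and the stratified hazard ratio and log-rank test are sound on this point.

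Size and direction cannot be derived from the documents, which give no control numbers, covariate shifts or control mortality. Under the assumptions tried, the false 8-month gap was about 0 to 13 points, with its sign set by which group has the better prognosis. Weighting left about 0 to 2 points.

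The effect is on how an exploratory sensitivity analysis would be read. The change is worth making because it replaces a potentially misleading display with a less biased one at low cost.

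**What to change.** For every PS-stratified OS and OS (Including PAV) comparison, in the FAS and the PPS, state in 4.7.1.3 and 4.7.1.4 that:

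1. The control Kaplan-Meier quartiles, survival rates and plot are computed with each control in PS stratum k weighted by (n_trt,k/N_trt)/(n_ctl,k/N_ctl), counted over the retained strata. Trehalose participants have weight 1.
2. Confidence intervals use a robust variance or a bootstrap. Say whether the bootstrap repeats the PS fit and the quintile cuts.
3. Any unweighted Kaplan-Meier output is labelled *unadjusted*.
4. The stratified hazard ratio and log-rank test stay as planned, with a note that they also stratify by bulbar onset, which enters the weights only through the PS.

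The cost is a short SAP addition, some programming and wider intervals for the control curve. By the usual approximation the effective control number is N divided by the sum over strata of 0.20²/share. In the middle case with 500 controls that sum is 0.04 × (1/0.50 + 1/0.20 + 1/0.15 + 1/0.10 + 1/0.05) = 1.75, giving 500/1.75 ≈ 286, still well above the 70 trehalose participants. A bootstrap that refits the PS takes more programming, because it must be repeated for each analysis set and OS definition. If no weighting is done, labelling the pooled curves as unadjusted is the minimum. It prevents misreading but leaves the comparison without adjusted survival figures.
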